During the *recruitment stage*, the RF H-reflex recruitment curve was achieved with the subject in a quiet standing posture. Electrical stimulation was delivered at 0.14 Hz only if the background EMG level of RF and MH were within a 10-20% MVC window respectively, representing a slight tonic voluntary activation to avoid altering reflex excitability. To find the maximum M-wave amplitude of the RF, we increased stimulation intensity by 2 mA increments starting at 10 mA until the RF M-wave amplitude remained constant despite increasing current in three successive stimulus intensities, defined as M_{max} . For each stimulus intensity, two H-reflex responses were recorded. The H-reflex size was calculated as the mean of the peak-to-peak amplitudes of the two responses. The corresponding intensity (I_{max}) that elicited maximal representative H-reflex (H_{max}) was used in the following trials. Post-stroke individuals did not require any additional support for standing, however for safety purposes a handrail was placed in front of the individual.

During the *stimulation stage*, also in performed in a standing posture, the femoral nerve was stimulated at I_{max} at 0.14 Hz based on the same 10-20% MVC requirement. The first 6 sessions were baseline sessions with no feedback of RF H-reflex. Each baseline session was composed of 3 runs of 75 trials, where each trial was a single stimulation pulse. The next 24 sessions were training sessions. During training, each session began with 20 control trials with no feedback, followed by 3 runs of 75 trials using the peak-to-peak magnitude of RF H-reflex as visual feedback to the participant (**Fig 1**). During training sessions trials, M-wave size was monitored, and stimulus strength (I_{max}) was minimally adjusted to maintain the predetermined M-wave size. Post-stroke

individuals participated in an additional 2 assessment sessions, one before training and one after training sessions. In participant H4, in two of the 30 training sessions, the H-reflex showed overlap with the M-wave. In offline analysis, we used a best decaying exponential fit to obtain the H-reflex estimate as illustrated in our earlier work.

FEEDBACK

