The two individuals with stroke participated in pre and post training assessment sessions. Participants performed a 10 m walk test (10MWT) with instructions to walk with maximum effort. This process was repeated 4 times and the participant's gait kinematics were recorded using inertial motion capture. Next, participants completed the quadriceps pendulum test, which is a non-invasive biomechanical method of evaluating spasticity using gravity to provoke muscle stretch reflexes during passive swinging of the lower limb. Inertial measurement units were attached on top of thigh, shank, and foot to calculate the knee joint angle during the process. This test was repeated 3 times with 30 second rest periods in between. The main outcome of this test was quadriceps reflex threshold angle (QRTA), which was the angle difference from the maximum knee extension position to the first swing excursion, the first transition period of knee flexion to knee extension. Lastly, the participant was asked to walk on an instrumented treadmill while their gait kinematics, ground reaction forces (GRF), and H-reflexes were obtained. During treadmill walking, four gait phases (heel-strike, toe-off, mid-stance, and mid-swing) were detected in real-time using online GRF data using conventional gait analysis¹. Heel-strike was detected when GRF value exceeded a predetermined force threshold (F_{th}) for the first time (0% gait cycle) and toe-off was detected with GRF dropping below the threshold (F_{th}) (60% gait cycle). Mid-stance was detected as the time point when 30% of step duration, pre-calculated from one's step length and gait speed, had elapsed from the moment of heel-strike. Mid-swing was determined in a similar

manner, which was detected at the 80% gait cycle. The H-reflex was elicited and measured only when a desired gait phase was detected and occurred at least 7 s after the last H-reflex trial. Twenty H-reflexes were recorded for each gait phase. A 5 min break after each of four runs was provided to minimize the effect of fatigue on H-reflex. The main outcomes consisted of 1) knee flexion range of motion (RoM), 2) peak knee flexion velocity, and 3) H-reflex amplitude during the four different gait phases.

OUTCOME MEASURES

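### Was the mid-stance H-reflex in the treadmill assessment triggered at 30% of a step instead of 30% of the gait cycle?

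*Combined protocol and SAP*

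**What the plan says.** The point lies in CLINICAL ASSESSMENTS, in the description of treadmill walking by the two stroke participants. Four gait phases trigger the femoral nerve stimulus.

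- Heel-strike and toe-off are read from the ground reaction force. Heel-strike is the force first exceeding a threshold, "for the first time (0% gait cycle) and toe-off was detected with GRF dropping below the threshold", and toe-off is labelled as 60% of the gait cycle.
- Mid-stance is timed: "Mid-stance was detected as the time point when 30% of step duration, pre-calculated from" the participant's step length and gait speed, "had elapsed from the moment of heel-strike".
- Mid-swing is also timed: "Mid-swing was determined in a similar" way, "which was detected at the 80% gait cycle".

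On volume, "Twenty H-reflexes were recorded for each gait phase". On status, the section lists "H-reflex amplitude during the four different gait phases" as one of three main outcomes of this part of the assessment. ACQUISITION AND PROCEDURES fixes the occasions: post-stroke "individuals participated in an additional 2 assessment sessions, one before training and one after training sessions".

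Step duration is not defined anywhere. STATISTICAL ANALYSIS names one test, a paired t-test of normalized H-reflex in the six baseline sessions against the last six training sessions. It names none for the gait-phase values.

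**The concern.** Three of the four phases are stated on the gait cycle and one on the step. A step is only part of a cycle, so 30% of a step always comes before 30% of a cycle. If the rule was applied as written, the reflexes labelled mid-stance were elicited in early stance.

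The phase is what gives each of these amplitudes its meaning, and the amplitudes are a listed main outcome. Someone repeating the study from this text could stimulate at a different point from the one intended. A trigger tied to the step would also move within the cycle if the participant's step symmetry changed between the two assessments.

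**Working it through.** **Inputs from CLINICAL ASSESSMENTS:** heel-strike 0%, toe-off 60% and mid-swing 80% of the gait cycle; mid-stance 30% of step duration; 20 reflexes per phase; four phases. **From ACQUISITION AND PROCEDURES:** two assessments per stroke participant. **Assumption, not in the documents:** the share *s* of the gait cycle taken by one step, 0.50 for equal steps, with a range of 0.35 to 0.65 for uneven gait.

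**1. Do the stated values fit the gait-cycle base?**

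- Middle of stance: (0 + 60)/2 = 30%.
- Middle of swing: (60 + 100)/2 = 80%.

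Both figures in the text are reproduced exactly, as percentages of the gait cycle.

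**2. Where would the triggers fall on a step base?** Position in the cycle = stated percentage × *s*.

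| *s* | 30% of a step | Share of the 60% stance elapsed | 80% of a step |
|---|---|---|---|
| 0.35 | 10.5% of cycle | 10.5/60 = 17.5% | 28% of cycle |
| 0.50 | 15.0% of cycle | 15/60 = 25% | 40% of cycle |
| 0.65 | 19.5% of cycle | 19.5/60 = 32.5% | 52% of cycle |

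Across this range the mid-stance trigger is early but still within stance. The last column tests the step reading. Mid-swing is said to be found in a similar way, yet on a step base it would fall before toe-off at 60%. To pass toe-off, a step would have to exceed 60/80 = 75% of the cycle. A rule that puts mid-swing inside stance is unlikely to have been the one used, and the text itself states mid-swing on the cycle.

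**3. What do the inputs to the duration imply?** Step length divided by speed is a step time, which favours the literal reading. The same quantities also give a cycle time, though: two step lengths divided by speed. The phrase does not settle which was computed.

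**4. How many values are involved?**

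- Per assessment: 20 × 4 = 80 reflexes.
- Step time used for mid-stance only: 20 of 80 (25%), which is 40 of 160 per participant over two assessments.
- Step time used for both timed triggers: 40 of 80 (50%), which is 80 of 160 per participant.
- Gait-cycle time used: none.

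**5. Does it reach the planned analysis?** The t-test uses standing reflexes from the baseline and training sessions. The treadmill reflexes come from the two additional assessment sessions and do not enter it.

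**The case for a change.** The strongest case for acting is that the documents cannot prove the wording is merely loose. The duration is said to come from step length and gait speed, which in plain arithmetic gives a step time. Replacing step duration with gait-cycle duration would not cure this, because the sentence would still derive a cycle time from a step length. The outcome is also called a main one.

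Nor is a pre-post comparison wholly protected by using the same rule twice. On the step base, a change in step share from 0.45 to 0.55 (an illustration; the documents do not report symmetry) would move the trigger from 30 × 0.45 = 13.5% to 30 × 0.55 = 16.5% of the cycle, a shift of 3 percentage points.

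What stands is that the sentence is ambiguous and that the base used cannot be established from the text. What does not stand is that the trigger was wrong. The midpoint arithmetic and the mid-swing check both point to the gait cycle. Even on the literal reading, the stimulus falls in stance at both assessments and the main defect is the name given to the phase. The possible shift in timing requires both the less likely reading and an unreported change in symmetry, and it concerns a descriptive measure in two people.

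**Conclusion.** The mismatch is real, but it is best read as a clerical slip, and no change to the plan follows. On the better-supported reading, in which step duration stands for gait-cycle duration, the effect is nil.

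On the literal reading with equal steps, the mid-stance stimulus falls at about 15% of the cycle (10.5% to 19.5% for assumed step shares of 0.35 to 0.65). That would affect the phase label of 20 of 80 reflexes per assessment, or 40 of 80 if mid-swing shared the step base.

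On either reading these values come from two participants, carry no planned test, and do not enter the comparison of baseline with late training on which the hypothesis rests. The document is written in the past tense, so altering the sentence would not move any stimulus already delivered. An author describing the method can name the base in passing; the design and the analysis stay as they are.

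This conclusion rests on the 0%, 60% and 80% landmarks meaning what they say, and on the same trigger rule having been used at both assessments, which the documents imply by describing only one.

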Study Title: Operant H-reflex Down-conditioning of Rectus Femoris in Post-stroke Stiff Knee
Gait

NCT number: NCT05467774

Document Date: 7/28/2021

SUBJECTS

A total of 7 participants (5 unimpaired [H1-H5, ages 20-26 years, 3 M/ 2 F], 2 post-stroke [S1-S2, 1 M/1 F] were recruited for this study. Each participant was able to stand for 10-minute intervals unassisted, walk on a treadmill for 10-minutes, and provide informed consent. Exclusion criteria included: lower limb musculoskeletal injury (e.g., fractures, sprains, strains, tendonitis, or bursitis), functionally relevant weight-bearing restrictions, vision impairment and must not have taken antispasmodic medication one day prior to the session. All 7 people participated in down-conditioning. The study was approved by the University of Texas Institutional Review Board, and all subjects gave informed consent prior to participation. Both post-stroke individuals had right hemiparesis and the experiment was conducted on the right side.

ACQUISITION AND PROCEDURES

The experimental setup consisted of 8-channel surface electromyography (EMG) sensors (AMT-8, Bortec, Calgary, AL), bipolar electrodes (Ag-AgCl, Noraxon, Scottsdale, AZ) a constant current electrical stimulator (Digitimer DS8R, Hertfordshire, UK), a data acquisition board (NI-PCIe 6321, Austin, TX), a desktop computer, and EPOCS software (**Fig 1**). Additionally, during assessment sessions, stroke subjects walked on an instrumented split-belt force treadmill (Bertec, Columbus, OH), during which the ground reaction forces (GRF) were recorded at 1kHz, and lower limb kinematic data were recorded via inertial motion capture (IMU, Xsens, Enschede, Netherlands) at 60 Hz.

The experiment was conducted over 30 experimental sessions per individual, with 3 sessions per week on non-consecutive days. To prevent diurnal variation in H-reflex magnitude, all training

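### Mid-stance and probably mid-swing walking reflexes are triggered after a pre-calculated delay, and the plan describes no check of the phase at which each stimulus landed

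*Combined protocol and SAP*

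**What the plan says.** The rules are in the combined protocol and SAP, Clinical Assessments. The general statement is that the four phases "were detected in real-time using online GRF data using conventional gait analysis". The individual rules are of two kinds.

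- **Force events.** Heel-strike is the first crossing of a force threshold (0% of the cycle), and "toe-off was detected with GRF dropping below the threshold" (labelled 60%).
- **Timed points.** "Mid-stance was detected as the time point when 30% of step duration", a duration worked out beforehand; the rest of that rule reads "step length and gait speed, had elapsed from the moment of heel-strike". For the last phase the text is "Mid-swing was determined in a similar", continuing over a page break with "manner, which was detected at the 80% gait cycle".

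Twenty reflexes are recorded per phase, so 20 × 4 = 80 per visit, once before and once after training. Reflex amplitude in the four phases is listed among the main outcomes of this assessment, beside knee flexion range and peak knee flexion velocity. Under Acquisition and Procedures, "the ground reaction forces (GRF) were recorded at 1kHz". Under Subjects, both stroke participants have right hemiparesis and the right side was tested.

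The plan does not state how step length was obtained, which leg it refers to, whether mid-swing is counted from heel-strike or toe-off, whether belt speed was the same at both visits, or whether the delay was recalculated after training. It describes no later check of where the stimuli fell.

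**The concern.** Each stride's heel-strike starts the clock, but the length of the wait is set in advance. The wait is right only if the pre-calculated duration matches the stride in progress. On a treadmill, stride time is the sum of the two step lengths divided by speed, so a duration built from one leg's step is wrong when the steps are unequal, which is a real possibility in hemiparesis. The 30% and 80% marks are also the midpoints of stance and swing only if toe-off falls at 60%.

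At stake is the reading of the before-and-after change in walking reflexes. If the stimulus samples a different part of the cycle at the second visit, a phase difference could be taken for a change in the reflex. Mid-swing is the more sensitive of the two phases and bears directly on stiff-knee gait. With two participants read individually, averaging across people cannot dilute a shift in timing.

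**Working it through.** **1. The plan's own phases.** With toe-off at 60% (Clinical Assessments), the midpoint of stance is 60/2 = 30% and the midpoint of swing is 60 + 40/2 = 80%. The nominal figures agree with each other if the 30% is a percentage of the whole cycle.

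**2. Step versus cycle.** The mid-stance rule refers to a step. With symmetric steps, a step is half a cycle, so 30% of a step is 0.30 × 50% = 15% of the cycle. The same rule at 80% would give 40%, which is before the stated toe-off. This inconsistency needs no assumed gait values. The steps below take the more favourable reading, that the whole cycle was meant.

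**3. Unequal steps.** Assumption: the cycle is taken as twice one leg's step. With r = that step divided by the other, the pre-calculated cycle T0 relates to the true cycle T by T0/T = 2r/(1 + r). A trigger aimed at p% and counted from heel-strike lands at p × T0/T. The ratios are assumed; the documents give none.

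| Step ratio r | T0/T | 30% lands at | 80% lands at |
|---|---|---|---|
| 1.0 | 1.000 | 30.0% | 80.0% |
| 1.2 | 1.091 | 32.7% | 87.3% |
| 1/1.2 | 0.909 | 27.3% | 72.7% |
| 1.5 | 1.200 | 36.0% | 96.0% |
| 1/1.5 | 0.800 | 24.0% | 64.0% |

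If both legs' steps are averaged, T0/T = 1 and this error is zero.

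**4. If mid-swing is counted from detected toe-off.** Only the last 20% of the cycle is then timed. With toe-off at 60%, r = 1.2 gives 60 + 20 × 1.091 = 81.8%, and r = 1/1.2 gives 60 + 20 × 0.909 = 78.2%. At r = 1.5 or 1/1.5 the results are 84% and 76%.

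**5. Between visits.**
- Delay recalculated each time from one leg's step, ratio changing from 1.5 to 1.2: 96.0 − 87.3 = 8.7 points of the cycle.
- Delay left unchanged, cycle 10% shorter after training: 80/0.9 = 88.9%.
- Delay recalculated each time from a correct two-leg stride time: no mean shift as a percentage of the cycle.
- Toe-off fraction changing to 65% or 70%: the swing midpoint becomes (65 + 100)/2 = 82.5% or (70 + 100)/2 = 85%, and the stance midpoint 32.5% or 35%, even with a correct stride time.

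**6. Stride-to-stride variation.** For an assumed stride-time CV of 3%, 5% or 8%, the SD of the realised phase at the 80% mark is 80 × CV = 2.4, 4.0 or 6.4 points. Under normal errors, 3.7%, 21% and 43% of stimuli miss by more than 5 points. The standard error of the mean phase over 20 reflexes is SD/√20, about 0.5 to 1.4 points over this range.

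**The case against.** The case against is substantial, and much of it stands.

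- **Source of the delay.** A reader might infer that the delay has nothing to do with measured strides. The text does not say that. Step length and speed are the participant's own and may have been measured, and heel-strike is detected on every stride, so error does not build up from stride to stride.
- **Mid-swing anchor.** A reader might infer that mid-swing is certainly not tied to toe-off. The plan says only that it was set in a similar way to mid-stance. Heel-strike is the likelier reading, but counting from toe-off is compatible with the text and reduces the error (step 4).
- **Shift between visits.** A reader might infer that the sampled phase did move after training. That depends on belt speed, recalculation and actual gait change, none of which the documents give.
- **Mechanisms.** Stride variability is mainly scatter. Over 20 reflexes it moves the mean phase by little and does not by itself produce a before-and-after difference. A toe-off fraction of 65–70% moves the swing midpoint by only 2.5–5 points from 80%.
- **Reach.** The single planned test, under Statistical Analysis, uses standing reflexes. No test is named for walking reflexes.

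The objection does not remove the pre-set delay, the clash between step and cycle, or the absence of any described check of the phase reached, in a main outcome of the stroke assessment.

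**Conclusion.** The concern holds in a limited form. Mid-stance is triggered after a pre-calculated delay, and mid-swing probably is too, so in hemiparetic gait the realised phase can differ from 30% and 80%. It can also differ between visits if step symmetry, cycle time or toe-off fraction changes. The mix of step and cycle is a defect of the text itself: read literally, with symmetric steps, mid-stance falls at about 15% of the cycle.

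The size of any timing error cannot be derived from the documents. The figure of 87% or 73% for an 80% trigger is an illustration. It rests on three assumptions: a step ratio of 1.2, a cycle taken as twice one leg's step, and counting from heel-strike. It vanishes if both steps are averaged and falls to about 82% or 78% if the count starts at toe-off and toe-off is at 60%.

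The scope is two of the four phases in the two stroke participants. The documents do not support a conclusion that the walking results are wrong, or that the standing H-reflex comparison is affected.

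**What to change.** 1. From the recorded forces and the logged stimulus times, compute each stimulus's realised phase against the actual heel-strikes and toe-off. Logging of stimulus times is assumed; the documents do not state it.
2. Report the mean and SD of realised phase at both visits, for each participant and each timed phase.
3. Compare walking reflexes before and after training by realised phase, re-binned or phase-matched, with the same rule at both visits.
4. Use any exclusion band only as a sensitivity analysis. As a deletion rule it could nearly empty the mid-swing cell: with the assumed CVs of 3–8%, a band of ±5 points around 80% keeps about 11–19 of 20 reflexes with equal steps, 3–7 at a ratio of 1.2, and 0–2 at 1.5.
5. State whether step or stride is meant, which leg supplied the step length, where the mid-swing count starts, and whether the delay was recalculated at the post-training visit.

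The cost is offline work on 80 stimuli per visit, using signals already recorded, and unequal numbers of reflexes per phase. No new data are needed.
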